7. HYPOTHESIS AND OBJECTIVES

This study is a retrospective registry of cases of CR to treatment with sunitinib in patients with metastatic renal cell carcinoma and has a purely descriptive purpose. Therefore, no previous hypothesis has been established.

7.1. Primary objectives:

To describe complete responses in daily clinical practice in Spain between 2007 and 30 October 2018, such as the documented disappearance of all lesions in the investigator's opinion on at least 2 consecutive CT scans.

To look for associations between CR from a macroscopic point of view and the baseline characteristics of both the patient and the tumour, such as:

- Demographic characteristics (age at the start of treatment)
- Comorbidities: cardiac, renal, endocrine, autoimmune and liver.
- Previous nephrectomy

- Classification of the risk group according to Motzer and/or Heng criteria and the association between each prognostic variable, such as: baseline patient status, time from nephrectomy to systemic treatment start, presence of anaemia, corrected calcium, LDH levels, neutrophil levels and platelet levels.
- Tumour data: histology, Fuhrman grade, presence of tumour necrosis and number and location of metastases (organs involved).

7.2. Secondary objectives:

- **To establish recommendations** to be followed **in patients who obtain CR to sunitinib treatment** based on the case recording and the adopted therapeutic strategy that obtained the greatest clinical benefit.
- To define **the median time on treatment with sunitinib until lesion complete remission is reached in the patient responsible physician opinion.**
- To define **the median duration of CR.**
- The time elapsed from the confirmation of CR to disease stabilisation/progression or change of treatment due to unacceptable toxicity or death from any cause will be collected.
- **The dose and treatment regimens used will be recorded.** In the case of changes in the treatment dose (increase or reduction), the reason (toxicity, efficacy, decision taken after lesion elimination or upon request of the patient) will be specified.
- **Description of local treatment techniques** if they were used and at what time they were applied. In the case of a pathology report on the resected part, the percentage of necrosis and histology will be recorded, as well as the surgical complications in the case that they arose.
- **Sunitinib treatment safety profile:** the adverse effects presented by the higher grade patients and whether the treatment had to be discontinued at any time due to toxicity will be recorded.
- In cases of systemic treatment discontinuation after a treatment period with CR maintenance, the reason for the decision and patient participation in this decision

(if the patient was consulted, if it was at his/her request or the investigator's decision).

- **Pharmacological group by mechanism of action used in patients on second-line treatment after disease progression:** another TKI, treatment with a drug that acts on the immune system.

7.3. Exploratory analysis:

Baseline neutrophil/leukocyte ratio and changes in neutrophil/lymphocyte ratio throughout treatment; after 4-6 weeks, at 3 months, at 6 months, at 9 months, 12 months, and then every 6 months in the laboratory tests available at approximately these dates.

8. METHODS OF INVESTIGATION

The purpose of this study is to describe in the routine practice setting, outside the clinical trial setting, the clinical characteristics of Spanish patients with metastatic renal cell cancer who have been receiving treatment with Sunitinib since it was marketed in 2007 until 30 October 2018, obtaining CR to treatment on their tumour documented with at least 2 imaging tests.

No hypothesis has been pre-specified, and all the study data will be analysed using descriptive statistical techniques.

8.1. Study design

Observational, retrospective, multicentre study in spanish patients with metastatic Renal Cell Carcinoma (mRCC) treated with sunitinib as a first-line treatment (treatment with previous cytokine therapy is accepted) according to clinical practice who obtained a complete response (CR) to treatment in one of these 2 situations:

- a) Complete response (CR) obtained exclusively with first-line sunitinib treatment (sunitinib CR).
- b) Response obtained after a period of time on treatment with sunitinib in which local treatment was also performed (surgery of the residual metastasis/metastases, radiofrequency ablation or radiotherapy) to achieve the total macroscopic disappearance of the disease, according to the opinion of the physician responsible for the patient (CR + local treatment).

8.2. Scope

The patient population eligible for this study includes any patient with advanced or metastatic renal cell cancer who has been treated with Sunitinib and has achieved CR of the tumour and its metastases at any time during treatment and according to the usual assessment criteria in daily clinical practice, whether it was obtained with sunitinib alone or if a local treatment was needed to eradicate all the lesions: (surgery of the residual metastases, radiofrequency ablation or radiotherapy)

The requirements for inclusion are:

1. These patients must have received Sunitinib as first-line treatment, according to their Summary of Product Characteristics.
2. Data collection: clinical, safety, response in patients with advanced renal cancer.

The study is expected to be conducted in 50 sites throughout Spain to reach the maximum number of patients in the registry.

The collection of cases will start at each hospital after the agreement with the site is signed and all study documentation has been completed and the person appointed by the sponsor delivers training on the procedures and objectives of the protocol.

As many patients at the site who meet the inclusion criteria and none of the exclusion criteria may be included.

This is an observational study designed to reflect routine clinical practice, there will be no interference with the routine daily medical care of patients with renal cancer.

The data collected will correspond to the data normally included in the medical records; demographic variables of the patients (never personal data that could lead to patient identification), age at the time of starting treatment, routine laboratory values required in the diagnosis and control of this condition, patient performance status and clinical status. It is also intended to collect treatment compliance, tolerability and adverse events and effectiveness of treatment.

As this is a retrospective observational study, no additional material or additional examinations not contemplated in regular practice will be required.

A patient who meets the inclusion criteria, who does not meet any exclusion criteria, and who has received treatment with sunitinib prior to participation in the registry will be considered assessable.

No patient follow-up period is established and there are no patient interviews, as there is only one time when the patient's data are reviewed; this will be when the investigator completes his/her CRF.

8.2.1. Inclusion Criteria

Patients must meet all the inclusion criteria described below to be eligible for the study:

1. Patients who are 18 year-old or over who have been treated for metastatic renal cell carcinoma with sunitinib as first-line treatment (treatment with prior cytokine therapy is accepted) between 2007 and 30 October 2018 and who have obtained as a best treatment response the total remission of the disease in the opinion of the doctor in charge from a clinical, radiological and/or macroscopic point of view. This response must have been reached through two possible strategies:
 - A) Systemic treatment with sunitinib alone.
 - B) Treatment with sunitinib and subsequent local treatment for one or more residual lesions that have not responded to the drug (traditional surgery, radiotherapy, SBRT (*Stereotactic Body Radiation Therapy*)).
2. The duration of CR must have been confirmed with at least 2 consecutive imaging tests, without having a limit in the duration of this response. Although the patient had progressed subsequently, he/she may be included in this registry.
3. Patients from any risk group
4. Tumours of any histology

The doctor responsible for the patient, in the event that he/she continues to attend routine reviews at the hospital, undertakes to send the patient a privacy alert according to the new EU legislation on personal data: regulation 2016/679 of the European parliament.

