NON-INTERVENTIONAL (NI) STUDY PROTOCOL

Study Information

Title	REGISTRY OF COMPLETE RESPONSES TO SUNITINIB IN SPANISH PATIENTS WITH METASTATIC RENAL CELL CARCINOMA (ATILA STUDY)
Protocol Code	A6181227
Protocol Version	Version 1.0 of 18 th October 2018
Date of the latest Protocol version	18 th October 2018
Active substance	Sunitinib Malate
Drug	SUTENT®
Objectives of the registry:	
To identify patients with metastatic renal cell carcinoma (mRCC) who obtained complete response (CR) to treatment with sunitinib alone or with sunitinib and a local treatment to eliminate residual disease and achieve CR in the clinician's opinion.
 
The clinical baseline characteristics of these patients and the tumour will be described in order to find predictive factors of response.
 
The aim is to describe the therapeutic strategy adopted in patients who obtained greater clinical benefit in the cases described once the macroscopic lesions have been eradicated in order to draft recommendations to follow once the statistical analysis of the registry is available.

PFIZER CONFIDENTIAL

Authors:

PPD MD PhD

Medical Oncologist

PPD

PPD MD

Senior Medical Advisor GU Pfizer

PPD

Pfizer Oncology Medical Department

Tel.: PPD

Email: PPD

This document contains confidential information belonging to Pfizer. Unless otherwise agreed in writing, on accepting or reviewing this document, you agree to keep this information confidential and not to copy it or disclose it to others (except when required by applicable law) or to use it for unauthorised purposes. In the event of any actual or suspected non-compliance with this obligation, Pfizer should be promptly notified.

TABLE OF CONTENTS

TABLE OF CONTENTS.....	3
1. LIST OF ABBREVIATIONS.....	5
2. PERSONS RESPONSIBLE FOR THE STUDY	9
3. ABSTRACT.....	10
4. AMENDMENTS AND UPDATES.....	16
5. MILESTONES.....	16
6. STUDY RATIONALE	17
7. HYPOTHESIS AND OBJECTIVES	26
7.1. Primary objectives:.....	26
7.2. Secondary objectives:.....	27
7.3. Exploratory analysis:.....	28
8. METHODS OF INVESTIGATION.....	28
8.1. Study design.....	28
8.2. Scope	29
8.2.1. Inclusion Criteria	30
8.2.2. Exclusion Criteria	30
8.3. Variables.....	31
8.4. Source documents.....	33
8.5. Sample size.....	33
8.6. Treatment of data.....	34
8.6.1. Case Report Forms (CRFs)/Data Collection Tools (DCTs)/Electronic Data Record.....	34
8.6.2. Records preservation.....	34
8.7. Data analysis	35
8.8. Quality control.....	35
8.9. Research methods limitations.....	36

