4.1.1. Inclusion Criteria

Patients must meet all the inclusion criteria below to be eligible for inclusion in the study:

[figure not shown]
1. Patients aged 18 years or older who have been treated for a metastatic renal carcinoma with first-line sunitinib in (prior cytokine treatment is admitted) between 2007 and October 30, 2018 and have obtained, as best response to treatment, total disease remission in the opinion of the treating physician from the clinical, radiological and/or macroscopic standpoint. This response must have been achieved through two possible strategies:
 - a. Systemic treatment with Sunitinib alone.
 - b. Treatment with Sunitinib and subsequent local treatment for one or several residual lesions that have not responded to the drug (traditional surgery, radiotherapy, SBRT (Stereotactic Body Radiation Therapy)).
2. The duration of the CR must have been confirmed by at least 2 consecutive imaging tests with no limit on the duration of this response. Patients with subsequent progression may be included in this registry.
3. Patients of any risk group.
4. Tumours of any histology.

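### Inclusion criterion 1B does not match the combined sunitinib-plus-local-treatment route in the design and scope: it adds a non-response condition, omits radiofrequency ablation and leaves timing open

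*Protocol*

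**What the plan says.** Inclusion criterion 1 (Protocol 8.2.1) asks for total remission as best response and adds: "This response must have been reached through two possible strategies". Route A is sunitinib alone. Route B is sunitinib and "subsequent local treatment for one or more residual lesions that have not responded to the drug", with traditional surgery, radiotherapy and SBRT given as the techniques. SAP 4.1.1 has the same condition: "subsequent local treatment for one or several residual lesions that have not responded to the drug". Protocol 8.2 and SAP 4.1 make a patient evaluable only if the inclusion criteria are met, so this wording decides who is analysed.

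The combined route is described differently elsewhere.

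- **Design** (Protocol 8.1(b), repeated in the Abstract and SAP 2.1): "Response obtained after a period of time on treatment with sunitinib in which local treatment was also performed", the techniques being "surgery of the residual metastasis/metastases, radiofrequency ablation or radiotherapy".
- **Scope** (Protocol 8.2): a patient who "has achieved CR of the tumour and its metastases at any time during treatment", whether with sunitinib alone or "if a local treatment was needed to eradicate all the lesions". Radiofrequency ablation is again listed.
- **Objective** (opening table of the protocol): CR with sunitinib alone or with "sunitinib and a local treatment to eliminate residual disease and achieve CR in the clinician's opinion". SAP 5 and 5.1 likewise speak of eliminating residual disease.

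**The concern.** The combined route is one of the two populations that the registry exists to describe. The clause that sites apply differs from the design on three points: how the lesion behaved on the drug, which local techniques count, and when local treatment took place. Around 50 sites will apply it to old charts, and sites that rely on different sections could register different patients.

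A loss would also be hard to see. The reasons for non-eligibility in SAP 7.2.1 include none for a patient who reached confirmed CR but fits neither route, so such patients would have no line in the planned table. For cases treated locally after sunitinib had stopped, two planned time variables lose their meaning.

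**Working it through.** The documents derive no figure on this point, so there is none to reproduce. The check sets the texts side by side, then gives a scale.

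**1. Comparison**

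| Feature | 1B (Protocol 8.2.1, SAP 4.1.1) | Design 8.1(b), SAP 2.1(b) | Scope 8.2 |
|---|---|---|---|
| Lesion | residual and not responding | residual | whatever remains to be cleared |
| Radiofrequency ablation | not listed | listed | listed |
| Timing | *subsequent* only | local treatment within the sunitinib period | CR reached during treatment |

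The SAP carries both the narrow wording (4.1.1) and the broad wording (2.1), so it does not settle the matter. The technique lists in SAP 7.2.2 and 7.2.4 follow 1B and also omit radiofrequency ablation.

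**2. Does a lesion that shrank count as having responded?** Table S3 in Protocol Section 6 counts partial response as response. In every column the objective response rate is complete plus partial response: 7 + 30 = 37, 1 + 27 = 28, 16 + 42 = 58, 1 + 21 = 22. On that usage, a lesion that shrank but persisted has responded.

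**3. Three test patients**

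- *Lesion shrinks, persists, and is resected on sunitinib.* Fails 1A (the drug alone did not clear it) and, read literally, fails 1B. Fits 8.1(b) and 8.2.
- *Residual lesion treated by radiofrequency ablation on sunitinib.* The technique is named in 8.1(b) and 8.2 but not in 1B.
- *Sunitinib stopped, residual lesion removed later.* Not barred by 1B or by the exclusions in 8.2.2. Does not fit the wording of 8.1(b), nor CR during treatment in 8.2.

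**4. Effect of the third case on the time variables.** Let S be the sunitinib start, E its definitive stop and C the CR date, with E before C.

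- Time on treatment until CR (SAP 7.2.4) = C − S = (E − S) + (C − E). The second term is time off the drug.
- Duration of sunitinib once CR is reached (SAP 5) = E − C, which is negative, or undefined if negative times are not allowed.

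**5. Scale.** Inputs: 28 of 64 CRs by the combined route in the single-hospital series (Protocol Section 6), and about 90 planned cases (Protocol 8.5).

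- Share: 28/64 = 43.75%, Wilson 95% interval 32.3% to 55.9%.
- Patients: 90 × 0.4375 = 39.4; interval 29.1 to 50.3.
- Loss on a literal reading: 39.4 × f, where f is the fraction whose treated lesion had shrunk. The documents do not give f. For f = 0, 0.25, 0.5, 0.75 and 1 the loss is 0, 9.8, 19.7, 29.5 and 39.4. These values show the range and none is an estimate.

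**The case against.** The strongest reply is that 1B can be read harmlessly. The same sentence is about total remission, so lesions that have not responded may simply mean lesions the drug did not clear, which agrees with the design. SAP 7.2.1 has no reason for non-eligibility based on lesion response, which suggests that the phrase was not meant as a separate screen. This stands in part: the fault is a conflict that allows a wrong exclusion, and exclusion is not certain. But *residual* already says that the lesion was not cleared, so on the harmless reading the extra phrase adds nothing, and the documents' own usage counts partial response as response.

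A reader might infer more than the text supports:

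- *That 1B rejects the typical combined-route patient.* No section says how residual lesions had behaved on sunitinib.
- *That 1B admits cases treated at any time after sunitinib which the scope excludes.* *Subsequent* can mean after the start of sunitinib and while still on it. 1B fails to bar off-drug cases but does not expressly admit them, and neither 8.2 nor 8.2.2 states such an exclusion.
- *That 1B causes the time-on-treatment problem.* SAP 7.2.4 subtracts calendar dates for every patient, so temporary interruptions are counted too. Off-drug cases make this worse, but it exists without them.
- *That removal of the primary tumour is a material gap.* 1B says lesions, which can include the primary. All patients in the single-hospital series and 96% in the Czech registry had been nephrectomised.

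The reply is also right that no new data item has been shown to be needed. SAP 5 collects the sunitinib start, interruption, restart and end dates, and Protocol 7.2 and SAP 7.2.4 plan to report when local treatment was applied.

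**Conclusion.** The mismatch is real and lies in the eligibility text. 1B adds a non-response condition found in no other description of the combined route, omits a technique that the design and scope name, and is looser than both on timing. Read literally, it turns away a patient whom Protocol 8.1(b) includes.

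About 39 of 90 cases (29 to 50) could enter through the clause. This assumes that the combined-route share in one hospital's series, in which 5 of 64 patients received sorafenib, carries over to this registry. The interval reflects sampling error in 28/64 only. The number lost on a literal reading could lie anywhere from none to all of these patients, and the number of off-drug cases cannot be estimated. The point therefore rests on the conflict between sections and not on a count of rejected patients.

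**What to change.** - In Protocol 8.2.1 (1B) and SAP 4.1.1 (1b), replace the non-response phrase with: *residual lesions persisting after a period of sunitinib, whether or not they had partially responded*.
- Add radiofrequency ablation to 1B in both documents and to the technique lists in SAP 7.2.2 and 7.2.4.
- Reconcile the timing wording of 1B with Protocol 8.1(b) and 8.2, and state one rule in all places. Which rule applies is for the sponsor to decide.
- From the dates already planned, derive a flag for sunitinib stopped before local treatment. Report flagged cases separately in time on treatment until CR and in duration of treatment after CR.

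These changes concern who is registered and how times are reported; no patient's care is affected. The cost is minor rewording in the two documents and one derived flag.

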8.2.2. Exclusion Criteria

Patients who meet any of the following criteria will not be included in the study:

PFIZER CONFIDENTIAL

1. Patients treated with another drug other than Sunitinib.
2. Patients with no radiology reports proving CR.
3. Patients with no record of the dose and regimen received with Sunitinib.
4. Patients who achieved complete remission after 30 October 2018.

Variables

ECOG	Eastern Cooperative Oncology Group	Risk groups
Age of the patient at the time of diagnosis	Epidemiological data	Years
TNM stage (T describes the size of the tumor and the spread of the cancer to nearby tissue; N describes the spread of the cancer to the nearby lymph nodes and the letter M describes the metastases)	Epidemiological data	Tumor stage
Histology of the tumor	Epidemiological data	Pathological anatomy
Tumor Fuhrman grade	Epidemiological data	Pathological anatomy
KPS	Karnofsky Performance Status	Risk groups
Previous nephrectomy	Epidemiological data	Surgery
Cardiac, renal, endocrine, autoimmune and hepatic comorbidities.	Epidemiological data	Disease data
Risk group classification	Epidemiological data	Risk groups
Baseline status of the patient	Epidemiological data	Risk groups
Time from nephrectomy to the start of systemic treatment	Epidemiological data	Risk groups
Hemoglobin	Epidemiological data	Risk groups
Calcium correction	Epidemiological data	Risk groups
LDH levels	Epidemiological data	Risk groups
Lymphocytes	Epidemiological data	Risk groups
Platelets	Epidemiological data	Risk groups

PFIZER CONFIDENTIAL

Neutrophil/lymphocyte index at baseline and after 6 weeks of treatment, at 3 months, at 6 months, at 9 months, at 12 months and then every 6 months	Epidemiological data	Risk groups
Number of metastases	Disease data	Disease data
Number of organs with metastasis	Disease data	Disease data
Median time with treatment before reaching the CR	Treatment data	Disease data
Median duration of the CR	Treatment/disease data	Disease data
Reason why CR ends: progression, tumor stabilization or intolerable toxicity	Disease data	Disease data
Doses and schemes of Sunitinib	Treatment data	Treatment data
Temporary treatment interruptions	Treatment data	Treatment data
Definitive treatment interruption after reaching CR	Treatment data	Treatment data
Active participation of the patient in the decision to definitively interrupt the treatment once the CR has been reached	Patient empowerment	
Time in Sunitinib treatment once the CR has been reached	Treatment data	Treatment data
Local treatment techniques of residual lesions	Treatment data	Treatment data
PA (pathological anatomy) of metastasectomy: histology and degree of necrosis	Disease data	Disease data
Adverse effects related to Sunitinib treatment of the highest degree achieved	Treatment data	Treatment data
Serious side effects (SAEs) during Sunitinib treatment	Treatment data	Treatment data
Pharmacological group of 2nd line treatment after disease	Treatment data	Treatment data

PFIZER CONFIDENTIAL

progression after a period of time in CR (TKI, mTOR, Immunotherapy)		
Cause of death	Disease data	Disease data

For this observational study, demographic variables that do not imply personal data with which the patient can be identified will be recorded, medical history including date and stage of the disease at diagnosis and progression, surgical treatment, histology, risk criteria for the disease before of its onset, comorbidities, blood and biochemical hematimetry, history of Sunitinib treatment, associated adverse events, clinical efficacy, dose, date of onset and subsequent treatments, as well as the patient's condition (alive, deceased), and date of last contact.

A full description of the variables, including the definitions, will be detailed in the Statistical Analysis Plan of the study. **Source documents**

The investigator will have full responsibility for the accuracy and authenticity of the clinical and laboratory data included in the CRFs at all times.

The source document of this study will be the patient's medical records in their clinical history, including their surgical records that will be kept at the centre where the study is conducted. All data will be captured in a CRF.

If special problems and/or questions arise or governmental requirements to carry out an inspection, it will be necessary to access, in addition, to the complete file of the study, as long as the right to anonymity of the patients is protected.

The information collected in the CRFs must match the data from the medical records.

